6.9. Prior and Concomitant Therapy

All concomitant treatments (both prescription and over-the-counter) taken during the study must be recorded with indication, daily dose, and start and stop dates of administration. All participants will be questioned about concomitant treatment at each clinic visit.

Treatments taken within 28 days before study intervention dosing on Day 1 will be documented as a prior treatment. Treatments taken after the first dose of study intervention will be documented as concomitant treatments.

Participants on certain medications are excluded from the study (see Appendix 9 for list of prohibited medications due to potential DDI and Appendix 10 for a list of other prohibited medications). Sites are encouraged to contact the sponsor should there be questions as to whether a medication is permitted or prohibited.

Females using hormonal contraceptives or taking hormone replacement therapy are eligible to participate in this study. See Appendix 4 for hormonal contraceptives that are permitted in this study.

Participants with T2DM and either normal renal function or renal impairment are permitted to be on stable doses of background medications for the management of their concomitant medical condition(s), as long as this is in line with protocol specifications regarding prohibited medications as described in this Section and in Appendix 9 and Appendix 10. On a case-by-case basis, with approval from the sponsor, participants receiving fluctuating concomitant medication/treatment may be considered if the underlying disease is under control. Whenever possible, attempts must be made to not add new medications or alter the doses and regimens of the concomitant medications after enrollment and for the duration of participation in this study, except in circumstances where a change is deemed medically necessary. Any changes must be captured in the CRF.

In addition, participants with T2DM using insulin are permitted to have sliding scale insulin or dose adjustment in insulin while confined to the CRU to attempt to maintain fasting and post-prandial glucose readings at similar levels that are achieved at home and based on the calories consumed while confined in the CRU.

Participants may receive permitted background medications according to their stable medication routine at their usual dosing times. This is with the exception of phosphate binders, antacids, and bile acid binding resins (eg, cholestyramine, colestipol), which must not be administered within the 8 hours before study intervention dosing on Day 1 or within the 4 hours after study intervention dosing. **On Day 1**, the investigator will determine the appropriate time to administer medications that are to be taken on an empty stomach. Otherwise, permitted concomitant medications that may be administered under fed conditions can be taken with breakfast on the morning of Day 1. On all other study days, participants are to receive their background medications at their usual times.

6.9.1. Rescue Medicine

There is no rescue therapy to reverse AEs observed with PF-07081532; standard medical supportive care must be provided to manage any AEs.

7. DISCONTINUATION OF STUDY INTERVENTION AND PARTICIPANT DISCONTINUATION/WITHDRAWAL

7.1. Discontinuation of Study Intervention

Since this is a single-dose study, this section is N/A.

7.2. Participant Discontinuation/Withdrawal From the Study

A participant may withdraw from the study at any time at their own request. Reasons for discontinuation from the study include the following: safety, behavioral, compliance or administrative reasons, or if the study is terminated by sponsor.

At the time of discontinuing from the study, if possible, an early discontinuation visit should be conducted. See the SoA for assessments to be collected at the time of study discontinuation and follow-up and for any further evaluations that need to be completed.

The early discontinuation visit applies only to participants who are enrolled/randomized and then are prematurely withdrawn from the study. Participants should be questioned regarding their reason for withdrawal.

The participant will be permanently discontinued from the study intervention and the study at that time.

If a participant withdraws from the study, they may request destruction of any remaining samples taken and not tested, and the investigator must document any such requests in the site study records and notify the sponsor accordingly.

If the participant withdraws from the study and also withdraws consent (see Section 7.2.1) for disclosure of future information, no further evaluations will be performed and no additional data will be collected. The sponsor may retain and continue to use any data collected before such withdrawal of consent.

7.2.1. Withdrawal of Consent

Participants who request to discontinue receipt of study intervention will remain in the study and must continue to be followed for protocol-specified follow-up procedures. The only exception to this is when a participant specifically withdraws consent for any further contact with them or persons previously authorized by the participant to provide this information. Participants should notify the investigator in writing of the decision to withdraw consent from future follow-up, whenever possible. The withdrawal of consent should be explained in detail in the medical records by the investigator, as to whether the withdrawal is only from further receipt of study intervention or also from study procedures and/or posttreatment study follow-up, and entered on the appropriate CRF page. In the event that vital status (whether the participant is alive or dead) is being measured, publicly available information should be used to determine vital status only as appropriately directed in accordance with local law.

7.3. Lost to Follow-up

A participant will be considered lost to follow-up if the participant repeatedly fails to return for scheduled visits and is unable to be contacted by the study site.

The following actions must be taken if a participant fails to attend a required study visit:

• The site must attempt to contact the participant and reschedule the missed visit as soon as possible. Counsel the participant on the importance of maintaining the assigned visit schedule and ascertain whether the participant wishes to and/or should continue in the study;

- Before a participant is deemed lost to follow-up, the investigator or designee must make every effort to regain contact with the participant (where possible, 3 telephone calls and, if necessary, a certified letter to the participant's last known mailing address or local equivalent methods). These contact attempts should be documented in the participant's medical record;
- Should the participant continue to be unreachable, the participant will be considered to have withdrawn from the study.

8. STUDY ASSESSMENTS AND PROCEDURES

8.1. Administrative Procedures

The investigator (or an appropriate delegate at the investigator site) must obtain a signed and dated ICD before performing any study-specific procedures.

Study procedures and their timing are summarized in the SoA. Protocol waivers or exemptions are not allowed.

Adherence to the study design requirements, including those specified in the SoA, is essential and required for study conduct.

All screening evaluations must be completed and reviewed to confirm that potential participants meet all eligibility criteria. The investigator will maintain a screening log to record details of all participants screened and to confirm eligibility or record reasons for screening failure, as applicable.

Participants will be screened within 28 days prior to administration of the study intervention to confirm that they meet the study population criteria for the study. If the time between screening and dosing exceeds 28 days as a result of unexpected delays (eg, delayed drug shipment), then participants may be rescreened after contact with a sponsor Clinical representative as described in Section 5.4.

Every effort should be made to ensure that protocol-required tests and procedures are completed as described. However, it is anticipated that from time to time there may be circumstances outside the control of the investigator that make it unfeasible to perform the test. In these cases, the investigator must take all steps necessary to ensure the safety and well-being of the participant. When a protocol-required test cannot be performed, the investigator will document the reason for the missed test and any corrective and preventive actions that they have taken to ensure that required processes are adhered to as soon as possible. The study team must be informed of these incidents in a timely manner.

If done around the time of a blood draw, ECGs and vital sign assessments (pulse rate, BP, and temperature) should be collected prior to any blood draw. If an IV catheter is utilized for blood sample collections, ECGs and vital sign assessments (pulse rate and BP) should be collected prior to the insertion of the catheter.

For samples being collected and shipped, detailed collection, processing, storage, and shipment instructions and contact information will be provided to the investigator site prior to initiation of the study.

The total blood sampling volume for individual participants in this study is approximately 150 mL. The actual collection times of blood sampling may change. Additional blood samples may be taken for safety assessments at times specified by Pfizer, provided the total volume taken during the study does not exceed 550 mL during any period of 56 consecutive days.

To prepare for study participation, participants will be instructed on the information in the Lifestyle Considerations and Concomitant Therapy sections of the protocol.

8.2. Efficacy Assessments

Not applicable.

8.3. Safety Assessments

Planned time points for all safety assessments are provided in the SoA. Unscheduled safety measurements may be obtained at any time during the study to assess any perceived safety issues.

8.3.1. Physical Examinations

A complete physical examination will include, at a minimum, head, ears, eyes, nose, mouth, neck, skin, heart and lung examinations, lymph nodes, and GI, musculoskeletal, and neurological systems.

A limited physical examination will include, at a minimum, assessments of general appearance, the respiratory and cardiovascular systems, and participant-reported symptoms.

Physical examinations may be conducted by a physician, trained physician's assistant, or nurse practitioner as acceptable according to local regulations.

Height and weight will also be measured as per the SoA and recorded in the CRF. For measuring weight, a scale with appropriate range and resolution is used and must be placed on a stable, flat surface. Participants must remove shoes, bulky layers of clothing, and jackets so that only light clothing remains. They must also remove the contents of their pockets and remain still during measurement of weight.

Physical examination findings collected during the study will be considered source data and will not be required to be reported, unless otherwise noted. Any untoward physical examination findings that are identified during the active collection period and meet the definition of an AE or SAE (Appendix 3) must be reported according to the processes in Sections 8.4.1 to 8.4.3.

8.3.2. Vital Signs

8.3.2.1. Blood Pressure and Pulse Rate

BP and pulse rate will be measured as defined in the SoA.

- Single, seated BP and pulse rate will be measured with the participant's arm supported at the level of the heart, and recorded to the nearest mmHg, following a seated rest of ≥5 minutes;
- Same arm (preferably the dominant arm) will be used for BP/pulse rate assessment throughout the study;
- BP/pulse rate assessment should not be taken from the arm with an IV catheter, if placed;
- Participants should be instructed not to speak during BP/pulse rate measurements.

The same properly sized and calibrated BP cuff will be used to measure BP each time. The use of an automated device for measuring BP and pulse rate is acceptable; however, when done manually, pulse rate will be measured in the brachial/radial artery for at least 30 seconds. When the timing of these measurements coincides with a blood collection, BP and pulse rate should be obtained prior to the nominal time of the blood collection.

Additional collection times, or changes to collection times, of BP and pulse rate will be permitted, as necessary, to ensure appropriate collection of safety data.

Any untoward vital sign findings that are identified during the active collection period and meet the definition of an AE or SAE (Appendix 3) must be reported according to the processes in Sections 8.4.1 to 8.4.3.

8.3.3. Electrocardiograms

Supine standard 12-lead ECGs utilizing limb leads (with a 10-second rhythm strip) should be collected at times specified in the SoA section of this protocol using an ECG machine that automatically calculates the HR and measures PR interval, QT interval, QTcF, and QRS complex. Alternative lead placement methodology using torso leads (eg, Mason-Likar) should not be used given the potential risk of discrepancies with ECGs acquired using standard limb lead placement. All scheduled ECGs should be performed after the participant has rested quietly for at least 5 minutes in a supine position.

To ensure safety of the participants, a qualified individual at the investigator site will make comparisons to baseline measurements. Additional ECG monitoring will occur if a) a postdose QTcF interval is increased by ≥60 ms from the baseline and is >450 ms; or b) an absolute QT value is ≥500 ms for any scheduled ECG. If either of these conditions occurs, then 2 additional ECGs will be collected 2-4 minutes apart to confirm the original measurement. If the QTcF values from these repeated ECGs remain above the threshold

value, then a single ECG must be repeated at least hourly until QTc values from 2 successive ECGs fall below the threshold value that triggered the repeat measurement.

If a) a postdose QTcF interval remains \geq 60 ms from the baseline and is >450 ms; or b) an absolute QT value is \geq 500 ms for any scheduled ECG for greater than 4 hours (or sooner, at the discretion of the investigator); or c) QTcF value get progressively longer, the participant should undergo continuous ECG monitoring. A cardiologist should be consulted if QTcF values do not return to less than the criteria listed above after 8 hours of monitoring (or sooner, at the discretion of the investigator).

In some cases, it may be appropriate to repeat abnormal ECGs to rule out improper lead placement as contributing to the ECG abnormality. It is important that leads be placed in the same positions each time in order to achieve precise ECG recordings. If a machine-read QTc value is prolonged, as defined above, repeat measurements may not be necessary if a qualified medical provider's interpretation determines that the QTcF values are in the acceptable range.

ECG values of potential clinical concern are listed in Appendix 8.

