10.8. Appendix 8: ECG Findings of Potential Clinical Concern

ECG Findings That May Qualify as AEs

- Marked sinus bradycardia (rate <40 bpm) lasting minutes.
- New PR interval prolongation >280 ms.
- New prolongation of QTcF to >480 ms (absolute) or by ≥60 ms from baseline.
- New-onset atrial flutter or fibrillation, with controlled ventricular response rate: ie, rate <120 bpm.
- New-onset type I second-degree (Wenckebach) AV block of >30 seconds' duration.
- Frequent PVCs, triplets, or short intervals (<30 seconds) of consecutive ventricular complexes.

ECG Findings That May Qualify as SAEs

- QTcF prolongation >500 ms.
- New ST-T changes suggestive of myocardial ischemia.
- New-onset LBBB (QRS complex>120 ms).
- New-onset right bundle branch block (QRS complex>120 ms).
- Symptomatic bradycardia.
- Asystole:
 - In awake, symptom-free participants in sinus rhythm, with documented periods
 of asystole ≥3.0 seconds or any escape rate <40 bpm, or with an escape rhythm
 that is below the AV node.
 - In awake, symptom-free participants with atrial fibrillation and bradycardia with 1 or more pauses of at least 5 seconds or longer.
 - Atrial flutter or fibrillation, with rapid ventricular response rate: rapid = rate >120 bpm.
- Sustained supraventricular tachycardia (rate >120 bpm) ("sustained" = short duration with relevant symptoms or lasting >1 minute).

- Ventricular rhythms >30 seconds' duration, including idioventricular rhythm (HR <40 bpm), accelerated idioventricular rhythm (HR >40 bpm to <100 bpm), and monomorphic/polymorphic ventricular tachycardia (HR >100 bpm [such as torsades de pointes]).
- Type II second-degree (Mobitz II) AV block.
- Complete (third-degree) heart block.

ECG Findings That Qualify as SAEs

- Change in pattern suggestive of new myocardial infarction.
- Sustained ventricular tachyarrhythmias (>30 seconds' duration).
- Second- or third-degree AV block requiring pacemaker placement.
- Asystolic pauses requiring pacemaker placement.
- Atrial flutter or fibrillation with rapid ventricular response requiring cardioversion.
- Ventricular fibrillation/flutter.
- At the discretion of the investigator, any arrhythmia classified as an adverse experience.

The enumerated list of major events of potential clinical concern are recommended as "alerts" or notifications from the core ECG laboratory to the investigator and Pfizer study team, and not to be considered as all-inclusive of what to be reported as AEs/SAEs.

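### Protocol 8.3.3 has no stand-alone absolute QTcF trigger for repeat ECGs: the 500 ms limb is written on QT, while the steps that follow it use QTcF or QTc

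*Protocol*

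**What the plan says.** Protocol 8.3.3 requires an ECG machine that "measures PR interval, QT interval, QTcF, and QRS complex", so QT and QTcF are two separate readings. Its rule then runs as follows.

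- **Trigger, limb (a):** "a postdose QTcF interval is increased by ≥60 ms from the baseline", and the value is also above 450 ms. Both parts are needed.
- **Trigger, limb (b):** "an absolute QT value is ≥500 ms for any scheduled ECG".
- **Confirmation:** two further ECGs 2 to 4 minutes apart, then "If the QTcF values from these repeated ECGs remain above the threshold" value, at least hourly ECGs.
- **Stop:** hourly ECGs continue "until QTc values from 2 successive ECGs fall below the threshold value that triggered the repeat measurement".
- **Continuous monitoring:** limb (b) again names an absolute QT value, "for any scheduled ECG for greater than 4 hours". A limb (c) covers QTcF that keeps lengthening.
- **Referral:** "A cardiologist should be consulted if QTcF values do not return to less than the criteria listed above" after 8 hours.
- **Overread:** a closing sentence allows the repeat to be skipped when a machine-read QTc is prolonged by the section's definition but a qualified provider judges QTcF acceptable.

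Appendix 8 sets its absolute limits on QTcF. A possible AE is "New prolongation of QTcF to >480 ms (absolute) or by ≥60 ms from baseline", and QTcF above 500 ms is a possible SAE. Protocol 9.3.3.1 tabulates uncorrected QT above 500 ms and, separately, QTcF above 500 ms. SAP 6.2.4 also summarises QT and QTcF as separate parameters.

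**The concern.** Limb (a) contains an absolute QTcF value, but only jointly with a 60 ms rise. Limb (b) is on QT. No limb therefore fires on a high absolute QTcF alone, although QTcF is the measure used in the confirmation step, the referral step and Appendix 8.

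QT shortens as heart rate rises, so above 60 bpm a QT below 500 ms can correspond to a QTcF above 500 ms. A participant who starts with a longish QTcF could reach the level that Appendix 8 lists as a possible SAE without meeting either limb. What would be lost is the protocol-required pair of repeat ECGs, and the hourly ECGs that may follow them.

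**Working it through.** **Inputs.** The thresholds (rise of 60 ms, QTcF 450 ms, QT 500 ms) are from Protocol 8.3.3, and the QTcF limits are from Appendix 8. The half-life of about 17 to 21 h, with sampling planned to allow for up to a doubling, is from Protocol 4.2. The heart rates and baseline values below are illustrative assumptions. The plan states no figure of its own to reproduce here.

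**Formula (Fridericia).** QTcF = QT / (60/HR)^(1/3), so QT = QTcF × (60/HR)^(1/3).

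**When both limbs stay silent.** At a QTcF of 500 ms or more the 450 ms part of limb (a) is already met, so limb (a) fails only if the rise is under 60 ms, that is, if baseline > QTcF − 60. Limb (b) fails if QT < 500, that is, if HR > 60 × (QTcF/500)³.

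| Post-dose QTcF (ms) | Limb (a) silent if baseline exceeds (ms) | Limb (b) silent if HR exceeds (bpm) |
|---|---|---|
| 500 | 500 − 60 = 440 | 60 × 1.00³ = 60.0 |
| 510 | 510 − 60 = 450 | 60 × 1.02³ = 63.7 |
| 520 | 520 − 60 = 460 | 60 × 1.04³ = 67.5 |

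**Worked case.** Take baseline QTcF 460 ms and post-dose QTcF 510 ms at 85 bpm. QT = 510 × (60/85)^(1/3) = 454 ms, below 500. The rise is 510 − 460 = 50 ms, below 60. Neither limb fires, yet 510 ms exceeds the Appendix 8 possible-SAE limit.

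**How far limb (b) sits from QTcF 500.** At 80 bpm, QTcF reaches 500 ms when QT is 454 ms. A QT of 500 ms at that rate is a QTcF of 500 / 0.75^(1/3) = 550 ms.

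**Low heart rates.** At 50 bpm, QT 500 ms is QTcF 500 / 1.2^(1/3) = 471 ms. Below 60 × 0.9³ = 43.7 bpm it is under 450 ms. Limb (b) then fires, but the QTcF confirmation step looks at a value already below 500 ms.

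**Exposure when the ECG is taken.** As far as the Schedule of Activities can be read, the scheduled post-dose ECG for completers is on Day 7 (144 h), with another at early discontinuation. Assuming simple exponential decline, the fraction of drug left at 144 h is 0.5^(144/17) = 0.3% to 0.5^(144/21) = 0.9%. If the half-life doubles to 42 h, it is 0.5^(144/42) = 9%.

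**Not computed.** The documents give neither the distribution of baseline QTcF nor the within-person SD, so the chance that a participant falls in the silent region cannot be estimated from them.

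**The case against.** The strongest reply is that the section itself treats its thresholds as corrected-QT thresholds. The overread sentence speaks of a QTc prolonged as already defined, and the confirmation, stop and cardiologist steps compare QTcF or QTc with those thresholds. On that reading limb (b) simply lost its suffix and the gap closes. This makes a slip likely, but it does not repair the text. Limb (b) says QT in two paragraphs of a section that lists QT and QTcF separately. The opposite defence, that QT is deliberate because Protocol 9.3.3.1 tabulates uncorrected QT above 500 ms, only confirms that an absolute QTcF limb is absent.

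A reader might go further and infer that dangerous prolongation would go undetected. The documents do not support that. Appendix 8 flags QTcF above 480 and above 500 ms, Protocol 8.3 allows unscheduled measurements, and Protocol 8.4.3 and Appendix 3 (10.3.3) oblige the investigator to follow AEs up. The repeat is also not absolute, because a qualified overread can waive it.

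A reader might also see a second safety gap at low heart rates, where a QT trigger is confirmed on QTcF. That mismatch is largely benign. A long raw QT is expected in bradycardia, and not starting hourly ECGs when QTcF is acceptable is sensible.

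**Conclusion.** The point holds as a minor wording fault in an operative safety rule. Taken literally, Protocol 8.3.3 requires no repeat ECG for a post-dose QTcF of 500 ms or more when the rise is under 60 ms and heart rate is above about 60 bpm. At exactly 500 ms this means a baseline above 440 ms. Exclusion criterion 15 in Protocol 5.2.1 removes clinically relevant ECG abnormalities but sets no numeric QTcF limit, so such baselines are not ruled out by number.

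The consequence is small. There appears to be one scheduled post-dose ECG per completer, when little drug remains. Protocol 2.2.4.1 reports no clinically significant adverse ECG trend at single doses up to 200 mg or 180 mg once daily, against a single 20 mg dose here. Detection and follow-up have other routes, and no PK endpoint is touched. The conclusion rests on reading QT in limb (b) as uncorrected and on a schedule table that is damaged in the available text.

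**What to change.** In both the repeat-ECG and the continuous-monitoring paragraphs of Protocol 8.3.3, put limb (b) on an absolute QTcF of 500 ms or more, or add that limb beside the QT one. In the stop step, write QTcF in place of QTc.

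Replacing QT is simpler but drops some present triggers, such as QT 500 ms at 50 bpm. If the QT limb is kept, call it uncorrected QT and let it prompt only the two confirmatory ECGs. Hourly repeats, continuous monitoring and cardiologist referral should then be decided on QTcF. Running those steps on raw QT could commit a bradycardic participant with an acceptable QTcF to hourly ECGs and a referral.

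The machine already reports both values, so no new measurement is needed. The cost is an occasional extra repeat ECG and a wording change. Protocol 10.1.1 requires IRB/EC approval of amendments, so the change is best carried in the next one.
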